Eligibility criteria	
Individuals who have symptoms consistent with pulmonary TB presenting to participating centres will be assessed and asked to participate. Participants will be categorised into 2 groups:
 
Case Detection group - Only participants who have not received any form of TB treatment within the prior 60 days will be enrolled.
 
Drug Resistant group – Non-converting TB cases presumed to be at risk of drug-resistance.

Primary outcomes	
1. Primary outcomes
 
1.1. Sensitivity of the Truenat MTB assays (including analysis by smear-status and by sample).
 
1.2. Specificity of the Truenat MTB assays (including analysis by sample).
 
1.3. Sensitivity of the Truenat MTB-RIF Dx assay.
 
1.4. Specificity of the Truenat MTB-RIF Dx assay.

Secondary outcomes	
2. Secondary outcomes
 
2.1. Sensitivity of the Truenat MTB assays and MTB-RIF Dx assay compared to Xpert MTB/RIF.
 
2.2. Specificity of the Truenat MTB assays and MTB-RIF Dx assay compared to Xpert MTB/RIF.
 
2.3. Patient important outcomes (see details in section Patient important outcomes under Statistical analysis plan).

Trial duration	Approximately 12 months
Time schedule	Trial start expected Q4-2018 with enrolment completion by Q2-2019. Follow-up after 2 months and testing of discordant cases completed Q4-2019.
GCP statement	All studies sponsored by FIND will be conducted in accordance with ICH-GCP Guidelines (ICH-GCP E6 R2), to the extent possible in the research setting as well as all national legal and regulatory requirements (as apply).

Schedule of Activities

Procedure	Enrolment		Follow-up visit 1	Notes
	Day 1	Day 2	Day 56 (±14)	
Informed consent	X			
Inclusion and exclusion criteria	X			
Demography	X			
Medical history (includes prior history of TB)	X			
Sputum sample collection	X	X*		
Blood sample collection (optional)	X			HIV testing will be offered to all participants as part of the trial procedures, unless a prior result is available (see Section 8)
AE/SAE review	←=====→			
Assess interval medication history			X	
 • Culture-negative, Truenat MTB (and/or MTB plus) and Xpert discordant cases. • 20% of Case Detection Group participants with negative results for all test, including culture

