8.3.2. Participant follow-up

A follow-up visit at Day 56 (+/- 14 days) post-enrolment will be conducted to a subset of participants in order to collect additional information on the TB status.

- **Culture-negative, Truenat MTB (and/or MTB plus) and Xpert discordant cases.** During the prospective assessment, Truenat results will not be provided to clinicians or participants or used for

decision-making. Thus participants who are Xpert-negative but Truenat-positive at enrolment (“discordant”) will not be treated on the basis of Truenat results. All culture negative cases with discrepant Truenat and Xpert results will undergo a follow-up visit performed at Day 56 (+/-14) post-enrolment to assess:

- Interval medication history, including TB treatment and clinical evolution.
- An additional spot sputum will be obtained for smear microscopy and culture (LJ and MGIT) provided the patient was not started on therapy and is able to provide a spontaneously produced sputum sample.

This will aid in the identification of patients who would be diagnosed (in the absence of Truenat MTB assays being available for decision making) on clinical grounds.

- **Cases Detection group with negative results.** The first 267 patients who are negative on all tests (approximately 20%) will be followed at Day 56 (+/-14) post-enrolment to assess:
 - Interval medication history, including TB treatment and clinical evolution
 - An additional spot sputum will be obtained for smear microscopy and culture (LJ and MGIT) provided the pulmonary symptoms persist and the patient was not started on therapy

The purpose of this follow-up visit is to identify the participants in this subset who are diagnosed/initiated on treatment on clinical grounds and those that are missed completely.

A follow-up visit is not required for participants who are started on treatment (based on Xpert or culture results).

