10.3. Populations for Analyses

For purposes of analysis, the following participant populations are defined:

Table 4. Populations for analyses

Population	Description
Enrolled	All participants who sign the ICF
Evaluable	All participants with a culture positive or culture negative results. Contaminated cultures will be excluded. Contamination is defined as below:
Smear-positive	≥ 1 positive smear (inclusive of scanty positive smears). Smear positives with only negative or contaminated cultures will be excluded from analysis.
Culture-positive	≥ 1 LJ and/or MGIT culture growth confirmed MTB complex. Cross-Contamination: A single LJ culture with ≤ 20 colonies or a single MGIT culture with MTB growth ≥28 days per patient will be excluded from analysis.
Culture-negative	At least 2 LJ or MGIT have no culture growth after >56 days and >42 days
Contaminated culture	LJ: Cultures completely overgrown by bacterial or fungal contaminations within 3 weeks (discarded). In case of mixed cultures, isolated MTB colonies transferred to new LJ tube (repeat culture). MGIT: Instrument positivity tests for confirmation of MTB complex negative. 2 contaminated cultures will lead to exclusion of this patient from analysis unless other criteria for culture-positivity/negativity are met
Xpert-positive	MTB positive on Xpert® MTB/RIF.
Xpert-negative	MTB negative on Xpert® MTB/RIF.
Xpert-indeterminate	Any indeterminate, error, or inability to produce a result from a single Xpert® MTB/RIF run.
Non-TB case	Smear-negative, Xpert-negative and culture-negative and not started on TB treatment on the basis of clinical criteria. NTM: Specimens with growth of mycobacteria other than MTB complex only.
Clinical TB case	Any participant who tests smear-negative, Xpert-negative, culture-negative but is started on TB treatment on the basis of clinical criteria.

Phenotypic RIF resistant	Culture-positive and growth for RIF on MGIT SIRE DST testing.
Phenotypic RIF sensitive	Culture-positive and no growth for RIF on MGIT SIRE DST testing
Genotypic RIF resistant	Sequencing identifies mutations recognized to be associated with RIF-resistance (defined based on consultation with WHO prior to analysis)
Genotypic RIF sensitive	Sequencing identifies no mutations recognized to be associated with RIF-resistance (defined based on consultation with WHO prior to analysis)

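### Table 4 splits Non-TB from Clinical TB by treatment start, which is scheduled for assessment only in a Day 56 subset chosen partly on the Truenat result; Section 10.5.2 should fix specificity on culture alone

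*Protocol*

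**What the plan says.** Protocol Section 10.3, Table 4, defines a Non-TB case as "Smear-negative, Xpert-negative and culture-negative and not started on TB treatment on the basis of clinical criteria" and a Clinical TB case as "Any participant who tests smear-negative, Xpert-negative, culture-negative but is started on TB treatment on the basis of clinical criteria". The test results are identical; treatment start alone separates the two classes.

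The Schedule of Activities places the assessment of interval medication history at Day 56 only. Section 8.3.2 limits that visit: "A follow-up visit at Day 56 (+/- 14 days) post-enrolment will be conducted to a subset of participants". The subset has two parts:

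- Discordants: "All culture negative cases with discrepant Truenat and Xpert results will undergo a follow-up visit".
- Negatives in the Case Detection group: "The first 267 patients who are negative on all tests (approximately 20%) will be followed at Day 56". The Schedule of Activities describes this part as "20% of Case Detection Group participants with negative results for all test, including culture".

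On the analysis side, Section 10.5.2 says that accuracy is analysed by the case definitions, and Table 6 takes false positives and true negatives from a column headed Non-TB. Objective 1.1 (Table 1) and Section 5.3.3 instead name culture as the reference standard for TB detection. The Evaluable row of Table 4 depends on culture results only, and Section 10.5.5 bases the specificity comparison with Xpert on cultures from S2 and S3.

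**The concern.** A class that depends on treatment start needs treatment start to be observed. For most all-negative participants no scheduled contact observes it. Ascertainment also depends on the index test: every participant who is Truenat-positive, Xpert-negative and culture-negative is due a visit, while only a minority of all-negatives are.

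If the Non-TB column of Table 6 is the Table 4 class, a false positive treated on clinical grounds will be found and moved to Clinical TB, out of the specificity denominator. Most true negatives treated on the same grounds will not be found and will stay in. That pushes specificity upward. If the column simply means culture-negative, treatment history plays no part. The protocol supports both readings, and specificity of the Truenat MTB assays is a primary endpoint.

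The class label is also used elsewhere. Section 11.6.1 links stored specimens to a final trial diagnosis that includes non-TB and clinical TB, so many all-negative specimens could carry an unverified label.

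**Working it through.** **Inputs from the protocol.** TB prevalence 20%; 1,333 participants before losses; 1,666 enrolled (Section 10.2); 267 all-negatives followed, given as approximately 20% (Section 8.3.2). The protocol does not give the number of culture-negative Truenat/Xpert discordants or the rate of clinical treatment starts. Both are assumed below.

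**Step 1: reproduce the 267.** 0.20 × 1,333 = 266.6, and 0.20 × 0.80 × 1,666 = 266.6. Both round to 267.

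**Step 2: share with no scheduled treatment assessment.** Culture-negatives = 0.80 × N. With a discordant share d, all of whom are visited, the unassessed share is 1 − d − 267/(0.80 × N).

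| N | Culture-negatives | 267 as share | Unassessed, d = 2% | Unassessed, d = 10% |
|---|---|---|---|---|
| 1,333 | 1,066 | 25.0% | 73% | 65% |
| 1,666 | 1,333 | 20.0% | 78% | 70% |

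The range is therefore about 65–78%. It treats attendance as complete.

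**Step 3: ascertainment by index result.** Truenat-positive/Xpert-negative/culture-negative participants: 100% by design. All-negatives: 267/[0.80 × N × (1 − d)]. For d from 0 to 5% this is 20.0–21.1% at N = 1,666 and 25.0–26.4% at N = 1,333, so about 20–26%. At d = 10% it is 22% and 28%. Treating every non-discordant culture-negative as an all-negative Case Detection participant is a simplification.

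**Step 4: effect on specificity if Table 4 governs (illustration).** Take 1,066 culture-negatives and assume that 3% are Truenat-positive/Xpert-negative (32 false positives, 1,034 true negatives), that 25% of these discordants start clinical treatment, and that 10% of the rest do. False positives left after removing treated ones: 32 × 0.75 = 24.

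- Treatment known for everyone: 1 − 24/(24 + 1,034 × 0.90) = 97.5%.
- Unvisited participants counted as Non-TB, so only 0.10 × 267 = 26.7 treated true negatives are removed: 1 − 24/(24 + 1,034 − 26.7) = 97.7%.

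Incomplete, index-dependent ascertainment adds about 0.2 percentage points. For comparison, the plain culture denominator gives 1 − 32/1,066 = 97.0% on the same inputs. The 0.5 points between 97.0% and 97.5% come from the change of definition, not from ascertainment.

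**Step 5: Clinical TB cases seen.** On the same assumptions the visits would find 0.25 × 32 + 0.10 × 267 = 35, out of 0.25 × 32 + 0.10 × 1,034 = 111.

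**The case against.** The strongest reply is that specificity is already fixed on culture. Objective 1.1, Section 5.3.3, the Evaluable row and Section 10.5.5 all point that way, and Section 10.5.2 presents Table 6 as the usual 2×2 layout. Moreover, the Table 4 Non-TB class requires a negative Xpert, so using it as the denominator would make Xpert specificity 100% by construction and empty secondary endpoint 2.1.2 of meaning. This makes the culture reading the more likely intention. It does not settle the text. Section 5.3.3 sends the reader to a case-definitions section for the RIF composite, and that composite is defined in Table 4, so the case definitions of Section 10.5.2 are naturally read as Table 4.

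Four further replies:

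- Section 12.2 lists treatment records and clinical status among the data captured, without limiting them to visited participants. This stands as a qualification: the gap is in scheduled assessment. The section gives no time point, window or participants.
- Section 10.4 leaves analysis populations and missing data to the SAP, which is not at hand. That is fair for the analysis method, but the class definition and the visit schedule are both set in the protocol, and an SAP cannot supply data that were not collected.
- Section 11.6.1 already names an Indeterminate diagnosis. It is not defined, and Table 4 does not contain it.
- Smear- or Xpert-positive culture-negatives belong to neither class whatever their treatment. This is correct: the classification gap concerns participants negative on smear, Xpert and culture.

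**Conclusion.** The point holds as an inconsistency worth correcting. The split in Table 4 cannot be made from scheduled data for most of the participants it is meant to divide, ascertainment depends on the index result, and the protocol leaves open whether that split defines the specificity denominator. The 65–78% rests on the protocol's 20% prevalence and an assumed 2–10% discordance. The bias of about 0.2 points rests on three assumed rates (3%, 25%, 10%) and arises only under the Table 4 reading.

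A reader might infer three stronger things, none of which the protocol supports:

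- That specificity would be badly distorted. If only visited participants could be Non-TB, the Step 4 inputs give 1 − 24/(24 + 267 × 0.90) = 90.9%, and 2–5% discordance gives about 83–94% across 1,066 to 1,333 culture-negatives. No section restricts the accuracy analysis to visited participants, and the Evaluable row and Section 10.5.2 speak against it.
- That a planned Clinical TB result would be wrong. No endpoint is a trial-wide Clinical TB count, and Section 8.3.2 confines the purpose of this follow-up to the subset itself.
- That unvisited participants can never be classified. The records listed in Section 12.2 might allow it; the protocol does not say.

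**What to change.** 1. In Section 10.5.2 and Table 6, state that specificity uses all evaluable culture-negative participants regardless of later treatment, and that Clinical TB cases are not removed from it. This agrees with objective 1.1 and Section 5.3.3 and removes the dependence on the index result.
2. In Table 4, assign Non-TB or Clinical TB only where treatment status was ascertained, and add a class for culture-negative participants whose treatment status was not assessed. If the treatment records in Section 12.2 are meant to cover everyone, give the date to which they run.
3. Report the Clinical TB proportion descriptively, separately for the discordants and for the followed all-negatives, noting that the latter are the first consecutive Case Detection participants and not a random sample.
4. Treat any weighting of the followed all-negatives up to the whole group as a sensitivity analysis only, with the assumption stated that early participants represent later ones. It should not extend to the Drug Resistant group, whose all-negative members have no planned follow-up and so cannot be represented by any weight.

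The cost is wording in Section 10.5.2, Table 4 and Table 6, with matching text in the SAP. No new visits or tests are needed. The price is that the Clinical TB proportion is reported for the followed strata only, not for the whole trial.

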5.3.3. Reference standard

Each participating laboratory will undergo an on-site laboratory evaluation to ensure standardized and high-quality performance of culture across sites (see also section Quality Assurance). Results from reference standard testing will be recorded blinded to index test results, eliminating the risk of review bias. Presence of MTB complex will be confirmed for all patients from a positive culture using MPT64 identification test and/or Line Probe Assay.

A reference standard of MTB culture (using two MGIT and two LJ cultures) will be used for TB detection. For RIF resistance detection a composite reference standard of phenotypic and genotypic RIF DST by sequencing will be used (as detailed in section Case definitions). This will allow for a high confidence in the interpretation of Truenat RIF resistant assay results. RIF sequencing will be done at a central laboratory for standardisation purposes (where possible).

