10.5.2. Analysis of Primary Outcomes

Analyses of the diagnostic accuracy of the index test will be done according to the case definitions. Table 6 summarizes the way diagnostic tests results are usually reported when comparing the index test results to a reference standard. Based on the definitions in the table, the following values are defined:

Sensitivity = $TP / (TP + FN)$

Specificity = $TN / (FP + TN)$

Table 6. Definition of classification metrics

Test result	Case definition			
		TB	Non-TB	Total
	Detected	TP	FP	TP + FP
	Not detected	FN	TN	FN + TN
	Total	TP + FP	FP + TN	All

Abbreviations: TB=true positive, FP=false positive, FN=false negative, TN=true negative

Only patients with uncontaminated culture results and without indeterminate test results will be included in the analysis of performance characteristics for MTB detection. Similarly, such patients will contribute to the analysis of the performance characteristics for RIF detection. For each point estimate, a 95% confidence interval will be derived based on Wilson score. Missing data and invalid results will be reported in the descriptive tables, and will not be imputed.

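### The protocol gives two incompatible denominators for specificity, and one of them makes Xpert specificity 100% by definition

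*Protocol*

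**What the plan says.** Two rules for the specificity denominator stand side by side.

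**Culture rule.** Section 5.3.3 states: "A reference standard of MTB culture (using two MGIT and two LJ cultures) will be used for TB detection". Objectives 1.1 and 2.1 (Section 2, Table 1), the opening of Section 10 and Section 10.1 also name culture, and Objective 2.1 and Section 10.1 do so for the comparison with Xpert. Section 10.5.5 bases the specificity comparison with Xpert on cultures. In Table 4 (Section 10.3) the Evaluable and Culture-negative rows depend on culture results only.

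**Case-definition rule.** Section 10.5.2, on the primary outcomes, states: "Analyses of the diagnostic accuracy of the index test will be done according to the case definitions". Table 6 there has the columns TB and Non-TB, and specificity uses the Non-TB column. The only definition of a Non-TB case is in Table 4: "Smear-negative, Xpert-negative and culture-negative and not started on TB treatment on the basis of clinical criteria". The same row adds a note on specimens growing only non-tuberculous mycobacteria (NTM), without an Xpert condition. Participants with all three tests negative who are treated on clinical grounds form a separate class, Clinical TB.

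Two further rules bear on who is counted. The Smear-positive row of Table 4 says: "Smear positives with only negative or contaminated cultures will be excluded from analysis". Section 8.3.2 says: "All culture negative cases with discrepant Truenat and Xpert results will undergo a follow-up visit performed at Day 56 (+/-14) post-enrolment". Among Case Detection participants who are negative on all tests, only the first 267 have that visit.

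**The concern.** Section 10.5.3 applies the same parameters to Xpert as to Truenat. If the Non-TB column is the denominator, the comparator is part of the reference standard against which it is judged. A culture-negative, Xpert-positive participant is neither Non-TB nor Clinical TB and drops out of specificity. Section 11.6.1 lists non-TB case among the final trial diagnoses, so the term is an operational class that an analyst could reasonably apply.

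At stake are primary endpoint 1.1.2 (Truenat specificity) and secondary endpoint 2.1.2 (specificity compared with Xpert), for which Table 5 plans a paired interval. The two rules give different estimates of both, and the trial is meant to inform policy recommendations.

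**Working it through.** **The plan's own figures.** Section 10.2 asks for 80 smear-negative, culture-positive cases, with TB prevalence 20% and 30% of TB cases smear-negative. 80 / (0.20 x 0.30) = 1,333, and 1,333 / 0.80 = 1,666. Both match the protocol. It states no expected specificity and no precision for it.

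**Expected culture-negatives.** 1,333 x 0.80 = about 1,066.

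**Formulas.** Among culture-negatives, let x be the Xpert false-positive rate, t the Truenat rate and b the rate of false positives on both.

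- Culture rule: Xpert specificity is 1 - x, Truenat specificity is 1 - t, and Truenat minus Xpert is x - t.
- Non-TB rule, considering Xpert status only: all Xpert-positives leave. Xpert specificity is TN / (0 + TN) = 100%. The Truenat false-positive rate becomes (t - b) / (1 - x), so the difference is -(t - b) / (1 - x), which cannot exceed 0.
- Truenat specificity rises only if (t - b) / (1 - x) < t, that is, if b / x > t. Truenat positivity must be commoner among Xpert-positive culture-negatives than among all culture-negatives.

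**Illustration.** The rates are assumptions: x from 1% to 3%, t one point higher, half of the Xpert false positives shared.

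| x | t | b | Difference, culture rule (points) | Truenat false-positive rate, Non-TB rule | Difference, Non-TB rule (points) | Truenat specificity |
|---|---|---|---|---|---|---|
| 1% | 2% | 0.5% | -1.0 | 1.5/99 = 1.52% | -1.5 | 98.0% to 98.5% |
| 2% | 3% | 1.0% | -1.0 | 2.0/98 = 2.04% | -2.0 | 97.0% to 98.0% |
| 3% | 4% | 1.5% | -1.0 | 2.5/97 = 2.58% | -2.6 | 96.0% to 97.4% |

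In counts for the middle row: 1,066 culture-negatives, 21.3 Xpert and 32.0 Truenat false positives, 10.7 shared; (32.0 - 10.7) / (1,066 - 21.3) = 2.04%.

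**Dependence on overlap, at x = 2% and t = 3%.**

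- No overlap: 3/98 = 3.06%. Truenat specificity falls slightly, from 97.0% to 96.9%, and the difference becomes -3.1 points.
- Independent errors: b = 0.06%, (3 - 0.06)/98 = 3.0%. Truenat specificity is unchanged.
- All Xpert false positives shared: 1/98 = 1.02%. The difference stays at about -1.0, but Truenat specificity rises to 99.0%.

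**The sign can change.** Take 32 Xpert and 21 Truenat false positives (about 97% and 98% specificity), 10 shared. The culture rule gives (32 - 21)/1,066 = +1.0 point; the Non-TB rule gives -(21 - 10)/(1,066 - 32) = -1.1 points.

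**Ascertainment of treatment.** All Truenat-positive, Xpert-negative, culture-negative participants have a Day-56 visit. Of participants negative on all tests, 267 do, which is 267/1,066 = 25% of the expected culture-negatives. Under the Non-TB rule, clinical treatment that moves a participant to Clinical TB is therefore more likely to be found in a Truenat false positive than in a true negative. The protocol gives no treatment rates, so this cannot be sized.

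**Smear exclusion.** A participant with a positive smear and negative cultures meets the Evaluable definition but is excluded by the Smear-positive row. This does not depend on which denominator is chosen. The protocol gives no expected number.

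**The case against.** The strongest reply is that culture is plainly the intended standard. It is named in at least five places, and for the Xpert specificity comparison specifically. Section 10.5.2 itself selects patients by uncontaminated cultures and determinate test results, without mentioning Xpert status or treatment. It introduces its table generically: "Table 6 summarizes the way diagnostic tests results are usually reported when comparing the index test results to a reference standard". Table 4 has no row called simply TB, so the headings of Table 6 do not map cleanly onto it. The case definitions could be read to include the Culture-negative row.

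Much of this stands. A reader might infer that the protocol has settled on an Xpert-conditioned specificity. The documents do not support that: what they contain is a contradiction. It still needs resolving, because the case-definition wording sits in the section governing the primary analysis and Non-TB has only one definition. An analysis plan may resolve it, but the protocol itself fixes both rules.

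A reader might also infer that Truenat specificity is inflated by construction. It is not. The inflation needs shared false positives. Section 7.1 makes them plausible, since molecular tests can detect DNA from nonviable bacilli, but with no overlap the estimate falls slightly.

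On treatment, Truenat results are withheld from clinicians, so the index result does not drive treatment; only its detection is uneven. The waiver of the visit for those treated on Xpert or culture results does not bear on this.

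**Conclusion.** The contradiction is real and should be corrected. Under the culture rule, Xpert can have false positives and endpoint 2.1.2 can be answered. Under the Table 4 and Table 6 rule, Xpert specificity is 100% by definition (the NTM note is the only possible exception) and the endpoint cannot be answered. This consequence needs no assumption about error rates.

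The numerical effects do. With the assumed rates and half of the Xpert false positives shared, the difference is 0.5 to 1.6 points more unfavourable to Truenat, and Truenat specificity is about 0.5 to 1.4 points higher, than under the culture rule. The upward bias is probable, not certain. The exclusion of smear-positive, culture-negative participants conflicts with the Evaluable definition under either reading, and the uneven ascertainment of treatment matters only if the Non-TB rule is used.

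**What to change.** - Relabel the Table 6 columns culture-positive and culture-negative.
- State in Section 10.5.2 that the specificity denominator, for Truenat and Xpert alike, is every participant who meets the Table 4 Culture-negative definition, whatever the smear result, Xpert result or later treatment. The existing handling of indeterminate test results can stay.
- In the Smear-positive row of Table 4, remove the exclusion of smear-positive, culture-negative participants from specificity. Those with only contaminated cultures remain excluded.
- Keep the Non-TB and Clinical TB classes for a labelled sensitivity analysis of Truenat only, and not for the comparison with Xpert.

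The cost is an edit to two tables and one sentence. Reported Truenat specificity may be slightly lower. The sample size does not change, because it rests on sensitivity in smear-negative, culture-positive cases.
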